10.4 Case Report Form Completion

Primary data collection based on source-documented hospital and/or clinic chart reviews will be performed clearly and accurately by site personnel trained on the CPSP and CRF completion. [REDACTED]

A large rectangular area of the page is completely blacked out, indicating that the original text has been removed or is not to be disclosed.

10.5 Record Retention

The Sponsor and Investigator/Site will archive and retain all documents pertaining to the CPS as per the applicable regulatory record retention requirements. The Investigator must obtain permission from Sponsor in writing before destroying or transferring control of any CPS records.

CONFIDENTIAL

A grid of 15 horizontal black bars of varying lengths on a white background. The bars are arranged in a staggered pattern, with some bars being longer than others. The lengths of the bars increase from left to right. The bars are positioned at different heights, with some being higher than others. The overall effect is a sense of depth and perspective.

CONFIDENTIAL

11.6 Benefit to Risk Rationale

While there are no additional risks associated with study participation, the public health may be benefitted.

CONFIDENTIAL

12. **ETHICAL CONSIDERATION**

12.1 Institutional Review Board/Ethics Committee Review and Approval

Institutional Review Board (IRB)/Ethics Committee (EC) approval for the CPSP and ICF/other written information provided to the patient will be obtained at each investigational site prior to consenting and enrolling patients in this clinical performance study. The approval letter must be received prior to the start of this clinical performance study and a copy must be provided to the Sponsor.

[REDACTED]

[REDACTED]

[REDACTED]

[REDACTED]

[REDACTED]

[REDACTED]

[REDACTED]

13. CLINICAL PERFORMANCE STUDY CONCLUSION

The clinical performance study will be concluded when:

- The investigational site is closed AND
- The final report has been provided to investigators or the Sponsor has provided formal documentation of clinical performance study closure.

The Sponsor shall submit the clinical performance study report (CPSR) within one year of the end of the investigation as applicable per the study.

CONFIDENTIAL

14. PUBLICATION POLICY

The data and results from the clinical performance study are the sole property of the Sponsor.

A series of horizontal black bars of varying lengths, with the fourth bar from the left being the longest.

[figure not shown]
CONFIDENTIAL

APPENDIX I: ABBREVIATIONS AND ACRONYMS

Abbreviation/Acronym	Words
AE	Adverse Event
ADE	Adverse Device Effect
CPS	Clinical Performance Study
CPSP	Clinical Performance Study Plan
CPSR	Clinical Performance Study Report
CRF	Case Report Form
CTA	Clinical Trial Agreement
DMP	Data Management Plan
EC	Ethics Committee
EDC	Electronic Data Capture
ICF	Informed Consent Form
IFU	Instructions For Use
IVD	In vitro Diagnostic
RT-PCR	Real-Time Polymerase Chain Reaction
PI	Principal Investigator
RAD	Rapid Antigen Detection
RDT	Rapid Diagnostic Test
SAP	Statistical Analysis Plan
SAE	Serious Adverse event

CONFIDENTIAL

CONFIDENTIAL

CONFIDENTIAL

Category	Magnitude
0	10
1	10
2	10
3	10
4	10
5	10
6	10
7	10
8	10
9	10
10	100
11	100
12	100
13	100
14	100
15	100
16	100
17	100
18	100
19	100

CONFIDENTIAL

[REDACTED]

[REDACTED]	[REDACTED]
[REDACTED]	[REDACTED]
[REDACTED]	[REDACTED] [REDACTED] [REDACTED] [REDACTED] [REDACTED] [REDACTED]
[REDACTED]	[REDACTED]

CONFIDENTIAL

CONFIDENTIAL

1. SYNOPSIS OF STUDY DESIGN

1.1 Purpose of Statistical Analysis Plan

This statistical analysis plan (SAP) is intended to provide a detailed and comprehensive description of the planned methodology and analysis to be used for the EuGeni SARS-CoV-2 Antigen Rapid Diagnostic Test Clinical Performance Study (CPS).

1.2 Clinical Performance Study Objectives

The objective of this CPS is to determine the diagnostic accuracy (sensitivity and specificity) of the EuGeni SARS-CoV-2 Antigen Rapid Diagnostic Test in the diagnosis of SARS-CoV-2 in specimens prospectively collected by healthcare professionals from subjects suspected of COVID-19 disease or with unknown COVID-19 status.

1.3 Clinical Performance Study Design

This CPS has been designed as a non-interventional, two-arm, prospective, non-randomized, open-label and multi-center study. Specimens can be prospectively collected by two different methods, which define the two arms of the study:

1. Nasopharyngeal specimen collection for comparison with gold-standard RT-PCR.
2. Combined nasal mid-turbinate and throat specimen collection for comparison with gold-standard RT-PCR.

1.4 Endpoints

1.4.1 Primary endpoint

The primary endpoint of this clinical performance study is to assess the EuGeni SARS-CoV-2 Ag RDT diagnostic accuracy, measured as the following:

- The diagnostic sensitivity of EuGeni SARS-CoV-2 Ag RDT, defined as the ability to identify the presence of a target marker associated with SARS-CoV-2, [REDACTED] compared with gold-standard SARS-CoV-2 RT-PCR.

CONFIDENTIAL

- The diagnostic specificity of EuGeni SARS-CoV-2 Ag RDT, defined as the ability to recognize the absence of a target marker associated with SARS CoV-2, [REDACTED] compared with gold-standard SARS-CoV-2 RT-PCR.

1.4.2 Secondary endpoint

The secondary endpoint of this clinical performance study is to compare the EuGeni SARS-CoV-2 Ag RDT diagnostic accuracy (specificity and sensitivity) between the two specimen collection methods (nasopharyngeal and combined nasal mid-turbinate and throat) [REDACTED]

1.5 Randomization

[REDACTED]
[REDACTED]
[REDACTED]
[REDACTED]

1.6 Blinding

[REDACTED]

CONFIDENTIAL

2. ANALYSIS CONSIDERATIONS

2.1 Analysis Populations

2.1.1 Per-protocol (PP) population

Per-Protocol (PP) population includes all specimens that meet the study eligibility and informed consent requirements. [REDACTED]

[REDACTED]

[REDACTED]

[REDACTED]

2.2 Statistical Methods

[REDACTED]

2.2.3 Survival analyses

Survival analyses do not apply to this CPS.

2.2.4 Regression

No regression analyses are planned for this CPS.

2.3 Endpoint Analysis

2.3.1 Primary endpoint(s)

The primary endpoint of this CPS evaluates the EuGeni SARS-CoV-2 Ag RDT diagnostic accuracy, which is defined in terms of sensitivity and specificity:

- The sensitivity is the ability to detect a target marker associated with SARS-CoV-2. The sensitivity means the capacity to detect positive samples from COVID-19 patients. [REDACTED]

[REDACTED]

[REDACTED]

[REDACTED]

- The specificity is the ability to recognize the absence of a target marker, associated with SARS-CoV-2, which means the capacity to detect true negative samples of COVID-19. [REDACTED]

[REDACTED]

CONFIDENTIAL

The evaluation of the primary endpoint will be performed using the PP population, analyzing the two arms of the study independently.

2.3.2 Secondary endpoint(s)

[REDACTED] This analysis will be performed through the comparison of the diagnostic sensitivity and diagnostic specificity values obtained from nasopharyngeal specimens and combined nasal mid-turbinate and throat specimens.

the differences between the specimen collection methods will be assessed by chi square statistical analysis, [REDACTED]

The evaluation of the secondary endpoint will be performed using the PP population, analyzing the two arms of the study independently.

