4.2.1 Informed Consent and Specimen collection

Before starting any study-related activity, the subject must have provided the signed informed consent form following the requirements in [Section 6.1.2]. Next, the specimen collection will be performed by professionally trained and qualified healthcare personnel.

CONFIDENTIAL

One bilateral swab will be taken to be analyzed with the device under investigation and another bilateral swab will be taken to be analyzed with the gold-standard RT-PCR. The specimen collection method for EuGeni analysis will be performed using either a combined nasal mid-turbinate and throat swab, or a nasopharyngeal swab, which will determine the inclusion into one of the two study arms. Enrolment into the combined nasal mid-turbinate and throat arm or nasopharyngeal will not be randomized, however consecutive and parallel enrollment in both arms will take place. Regardless of the study arm, the RT-PCR specimen collection will always occur to allow result comparison between the investigational device and RT-PCR.

For further information on specimen collection, please refer to IFU [REDACTED]

[figure not shown]

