4.3 Measures Taken to Avoid and Minimize Bias

This clinical performance study has been designed to be multicenter in order to minimize bias related to site specific standard of care patient and specimen collection method.

All participants who meet the inclusion and exclusion criteria will be eligible to join the study. Inclusion into the two study arms will not be randomized, however sites will be instructed to consecutively enroll subjects into both arms. Recruitment at each investigational site will be limited to █ of the total sample size.

To avoid bias related to the collection method, all study subjects will have a bilateral swab specimen collection for investigational device analysis and for RT-PCR analysis, for direct comparison within the same subjects.

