5.2 Secondary Endpoint

The secondary endpoint of this clinical performance study is to compare the EuGeni SARS-CoV-2 Ag RDT diagnostic accuracy (specificity and sensitivity) between the two specimen collection methods (nasopharyngeal and combined nasal mid-turbinate and throat) to assess any potential impact on diagnostic accuracy.

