8.2.2 Secondary Endpoint Analysis

The secondary endpoint assesses any potential impact of the specimen collection method (arms 1 and 2) on EuGeni SARS-CoV-2 Ag RDT diagnostic accuracy (specificity and sensitivity rates). [REDACTED]

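### The secondary endpoint compares two non-randomised swab arms with a chi-square test and no visible case-mix stratification, so systematic differences in who enters each arm could mimic or hide a swab effect.

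*SAP*

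**What the plan says.** Protocol 5.2 compares sensitivity and specificity between the two collection methods "to assess any potential impact on diagnostic accuracy". Protocol 8.2.2 repeats the aim: "The secondary endpoint assesses any potential impact of the specimen collection method".

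Protocol 4.2.1 allows two ways of taking the device specimen, the combined method "or a nasopharyngeal swab, which will determine the inclusion into one of the two study arms". That section adds that allocation "will not be randomized, however consecutive and parallel enrollment in both arms will take place". Protocol 4.3 says the same: "Inclusion into the two study arms will not be randomized, however sites will be instructed to consecutively enroll subjects into both arms". It also caps recruitment at each site (value redacted) and provides paired swabs "for investigational device analysis and for RT-PCR analysis, for direct comparison within the same subjects".

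Protocol 4.1 sets the same targets in each arm: 300 positives, 120 hospitalised negatives and 505 negatives with respiratory symptoms. It calls these numbers approximate.

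For the analysis, SAP 2.3.2 says "the differences between the specimen collection methods will be assessed by chi square statistical analysis", and the rest of that sentence is redacted. SAP 2.2.4 adds: "No regression analyses are planned for this CPS". SAP 2.9 lists Ct value and days from symptom onset as possible subgroups, with no visible link to the comparison between arms.

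**The concern.** The question is about the effect of the swab, but the visible method is a crude comparison of two self-contained groups. The pairing in Protocol 4.3 is device against RT-PCR within a subject. It does not pair one swab type with the other, so it does nothing to balance the arms. No visible rule says which subject gets which swab.

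If one arm systematically receives more late presenters, or a different mix of hospitalised and symptomatic negatives, the chi-square can show a swab difference that does not exist or miss one that does. Chance imbalance is not the issue, because it leaves the test at 5%.

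The primary endpoint is not at stake: SAP 2.3.1 assesses each arm separately against RT-PCR.

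**Working it through.** **Inputs from the documents.** Per arm there are 300 positives and 120 + 505 = 625 negatives, so 2 × (300 + 120 + 505) = 1850, which matches the stated total. The hospitalised share of negatives is 120/625 = 19.2%. The targets are 80% sensitivity and 98% specificity (SAP 2.4).

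**Assumptions.** The documents show no alpha, no onset gradient and no imbalance. I assume a two-sided 5% level, two onset bands, and gradients that give 80% sensitivity at a 20% late share. Shifts are in the underlying mix, so chance imbalance is already included in the equal-mix results. Simulations use 40,000 replicates and compare the Pearson chi-square with CMH, without continuity correction.

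**1. False positives with no swab effect.** With late share w, crude sensitivity in an arm is (1 − w) × early + w × late. The spurious difference is therefore (w_B − w_A) × (early − late). For 84/64 and 20% against 30% late:

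- Arm A: 0.8 × 84 + 0.2 × 64 = 80.0%. Arm B: 0.7 × 84 + 0.3 × 64 = 78.0%.
- SE = √(0.80 × 0.20/300 + 0.78 × 0.22/300) = 0.0332, so δ/SE = 0.60.
- Rejection ≈ Φ(0.60 − 1.96) + Φ(−0.60 − 1.96) = 0.087 + 0.005 = 9.2%. Simulation gives 9.3%.

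| Early/late sensitivity | Spurious difference at 20% v 30% | Chi-square, 20% v 20% | 20% v 25% | 20% v 30% | CMH, 20% v 30%, onset band wrong in 10% / 20% |
|---|---|---|---|---|---|
| 82/72 | 1 point | 5.0% | 5.2% | 6.2% | 5.1% / 5.4% |
| 84/64 | 2 points | 5.1% | 6.0% | 9.3% | 5.7% / 7.2% |
| 86/56 | 3 points | 4.9% | 7.5% | 14.5% | 6.7% / 9.8% |
| 90/40 | 5 points | 5.0% | 11.9% | 30.7% | 10.7% / 18.9% |

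With onset recorded correctly, CMH stays at about 5% throughout. With misrecorded onset it reduces confounding but does not remove it.

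**2. Masking.** Suppose one method is truly 8 points less sensitive and its arm has 10% rather than 20% late presenters. The crude difference shrinks to 8 − 0.10 × (early − late), that is 7, 6, 5 or 3 points. Chi-square power is then 53%, 42%, 32% or 15%, against 63% with equal mixes. CMH gives 63%, 65%, 68% or 75%.

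**3. Specificity.** Suppose 240 rather than 120 of one arm's 625 negatives are hospitalised (38.4% against 19.2%).

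- At 95% (hospitalised) and 98.7% (symptomatic), the spurious difference is 0.192 × 3.7 = 0.7 points and the chi-square rejects in 13%. With 180 hospitalised it rejects in 7%.
- At 97.5% and 98.2%, the difference is 0.192 × 0.7 = 0.13 points and the chi-square rejects in 5% with either 180 or 240.

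Specificity is therefore little affected unless both the shares and the stratum specificities differ markedly.

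**The case against.** The strongest objection is that the gap may come from redaction. The chi-square sentence is cut off, Protocol 8.2.2 is hidden after its first sentence, and SAP 1.5 and most of SAP 2.2 are hidden. Parts of SAP 2.9 and 3.5 are redacted, and SAP 2.5, 2.6, 2.8 and 2.10 to 2.13 cannot be seen. Stratification could be in any of these. The redaction after the positive-specimen targets in Protocol 4.1 could also fix onset bands per arm, which would largely prevent the 20% against 30% scenario. This stands as a limit on certainty, so the request is conditional.

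Next, the visible safeguards are real: consecutive and parallel enrolment, identical targets and a site cap. No passage shows a mechanism that sends late presenters to one arm. That lowers the likelihood of bias but does not exclude it. The visible text fixes no onset mix by arm. Protocol 4.1 lets numbers vary with recruitment; its stated purpose of reaching the right sample distribution does not settle that mix either. The site cap limits a site's total, not its split between arms.

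Finally, the magnitudes are assumed. At a 5-point shift in late share, three of the four gradients give only 5.2% to 7.5%, and 31% needs a 50-point gradient with a 10-point shift. CMH holds 5% here because onset is the only confounder simulated. These points are correct. They limit the claim to a plausible bias in a secondary endpoint.

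**Conclusion.** The concern holds. On the visible text, a question about the effect of collection method is answered by an unadjusted comparison of non-randomised arms. A systematic difference in case mix could produce or conceal a sensitivity difference. In the illustrations, false-positive rates run from 5% to 31%, and power for a true 8-point loss falls from 63% to between 53% and 15%. These figures rest on assumed gradients and shifts and are not predictions for this study. Specificity is a minor issue.

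This should be fixed before analysis, but it does not threaten the study's main result. Confidence is medium, because hidden text may already deal with it.

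**What to change.** In SAP 2.3.2, unless the redacted text already does this:

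1. Report the between-arm difference as a Mantel-Haenszel risk difference with 95% CI and a CMH test. Stratify sensitivity by pre-specified days-from-onset bands, and specificity by hospitalised or symptomatic stratum. Add coarse site groups only where cells are not sparse and each group enrolled both arms in reasonable numbers. At 98% specificity only 625 × 0.02 = 12.5 false positives per arm are expected.
2. Tabulate onset, site, stratum and Ct by arm.
3. Keep the chi-square, labelled as an unadjusted association, and describe the result as a non-randomised comparison with possible residual confounding.
4. Use Ct strata only as a sensitivity analysis, and only if RT-PCR sampling does not differ by arm. The visible text does not say whether it does.
5. Editorial: the closing sentence of SAP 2.3.2 repeats the primary endpoint's wording that the arms are analysed independently. For this endpoint it should say that the arms are compared.

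SAP 2.2.4 can stay, because CMH is not a regression.

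**Cost.** This needs SAP wording, one table, a little code, and confirmation that onset is recorded for every positive. Stratifying by onset alone costs almost no precision: the mean 95% CI half-width is 5.5 to 6.8 points, against 6.4 to 6.8 unadjusted.

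Site strata can cost more. The figures below come from simulation (20,000 replicates) with 3 to 10 equal sites and the arm split alternating between sites. Sensitivity uses 84/64 with 20% against 30% late; specificity is 98% in all strata.

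| Arm split within sites | Sensitivity half-width (6.5 unadjusted) | Specificity half-width (1.5 unadjusted) |
|---|---|---|
| Even | 6.4 to 6.5 points | 1.6 points |
| 70/30 | 6.9 to 7.1 points | 1.7 points |
| 90/10 | 10.1 to 10.7 points | 2.4 to 2.6 points |

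The main loss comes from sites that enrol mostly one arm.

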2.4 Sample Size Calculations

The sample size calculation is based on the objective to demonstrate an 80% sensitivity and a 98% specificity of the EuGeni SARS-CoV-2 Ag RDT for COVID-19 testing, [REDACTED]

Term	Percentage
GMOs	85%
Organic	75%
Natural	70%
Artificial	45%
Organic	80%
Natural	75%
Artificial	50%
Organic	85%
Natural	80%
Artificial	55%
Organic	70%
Natural	65%
Artificial	40%
Organic	60%
Natural	55%
Artificial	35%
Organic	50%
Natural	45%
Artificial	30%
Organic	40%
Natural	35%
Artificial	25%
Organic	30%
Natural	25%
Artificial	15%

CONFIDENTIAL

2.7 Timing of Analysis

In addition to the interim analysis described above, the study endpoints will be assessed after all specimens are processed and analyzed by both the investigational device and the gold-standard RT-PCR technique, [REDACTED]

2.9 Subgroups of Analysis

Subgroup analyses in the context of this CPS will be performed [REDACTED]

[REDACTED] according to different specimen characteristics, which may include:

- The viral load, determined by the Ct value obtained in the RT-PCR analysis.
- [REDACTED]
- Days from symptom onset. [REDACTED]
- [REDACTED]

- [REDACTED]
- [REDACTED]
- [REDACTED]

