1.1 Background and rationale

In 2019 a novel corona virus, designated as SARS-CoV-2 and associated with unusual viral pneumonia named Corona virus Disease 19 (COVID-19), sprouted in the city of Wuhan, China, and rapidly spread to create a global pandemic. Identification of people infected with severe acute respiratory syndrome coronavirus 2 (SARS-CoV-2) is essential for controlling its spreading and public health management.

Since the beginning of the COVID-19 outbreak, tests that can enable both mass screening and reliable detection of infected people are needed¹. The reliance on testing underscores the importance of analytical sensitivity of virus assays, being the real-time quantitative polymerase chain reaction (RT-qPCR) from nasopharynx swab the gold-standard². However, RT-PCR is expensive, time-consuming, and requires specialized laboratory personnel and instrumentation compared to rapid tests³.

New developments in SARS-CoV-2 diagnostics have the potential to reduce cost and turnaround time⁴⁻⁶. Several diagnostic strategies are available for identifying or ruling out current infection, identifying people in need of care escalation, or testing for past infection and immune response. Point-of-care (POC) antigen and molecular tests for the detection of current SARS-CoV-2 infections are rapid antigen detection (RAD) tests, which allow earlier detection and isolation of confirmed cases compared to laboratory-based diagnostic methods.

Coronavirus RAD tests, have demonstrated good sensitivity and specificity in comparison to RT-qPCR⁷⁻⁹. Moreover, previous studies have shown that RADs can exhibit high sensitivity in detecting samples containing infectious virus, indicating a high sensitivity to detect contagious individuals^{10,11}.

The RAD tests, based on the immunochromatographic principle, detect SARS-CoV-2 nucleocapsid protein (N) at or near the place where a specimen is collected, providing results within few minutes³. In general, RAD tests consist of fixing match-paired antibodies to the surface of the cassette and coupling an anti-antigen match-paired antibodies to the detection nanoparticles.

[REDACTED]

[REDACTED]

[REDACTED]

[REDACTED]

[REDACTED]

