4. CLINICAL PERFORMANCE STUDY DESIGN AND PROCEDURES

4.1 Clinical performance study design

This clinical performance study (CPS) is designed as a non-interventional, two-arm, prospective, non-randomized, open-label and multi-center study. The two study arms as defined depending on the specimen collection method:

1. Nasopharyngeal specimen collection for comparison with gold-standard RT-PCR
2. Combined nasal mid-turbinate and throat specimen collection for comparison with gold-standard RT-PCR

The expected minimum number of specimens for this CPS is 1850, divided as follows:

Nasopharyngeal specimen collection:

- 300 positive specimens collected from subjects at different timepoints post onset of symptoms: [REDACTED]
- 120 negative specimens from hospitalized patients
- 505 negative specimens from subjects with respiratory symptoms

Combined nasal mid-turbinate and throat specimen collection:

- 300 positive specimens collected from subjects at different timepoints post onset of symptoms: [REDACTED]
- 120 negative specimens from hospitalized patients
- 505 negative specimens from subjects with respiratory symptoms.

[REDACTED] The estimated numbers for each specimen type are approximate and may vary depending on the natural recruitment at the investigational sites to ensure the correct distribution of sample size requirements.

The study has been designed to involve as little pain, discomfort, fear and any other foreseeable risk as possible for the subjects, and both the risk threshold and the degree of distress are specifically defined in the clinical performance study plan (CPSP) and constantly monitored.

The CPS will be conducted in up to 10 sites in Europe. The primary and secondary endpoints will be evaluated when all specimens have been collected and analyzed. [REDACTED]

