4.2.2 Specimen analysis procedure

The specimen analysis shall be performed by professional healthcare personnel. Specimens to be analyzed by the gold-standard RT-PCR shall follow the procedures established by the standard of care. [REDACTED]

Those specimens analyzed by the EuGeni SARS-CoV-2 Antigen Rapid Diagnostic Test shall follow the procedures laid down in the IFU and protocol. [REDACTED]

- a) Positive results indicate the presence of SARS-CoV-2-antigen and is indicative of primary SARS-CoV-2 infection. [REDACTED]
- b) Negative results indicate the specimen does not contain SARS-CoV-2 antigen. In this case, only the [REDACTED] control line will be displayed. Negative results should be treated as presumptive and should not be used as the sole basis for clinical diagnosis and treatment. [REDACTED]
- c) If a test is Invalid, a new test should be performed with a new subject specimen and a new cassette. [REDACTED]

For more information on the interpretation of results, please refer to the EuGeni SARS-CoV-2 Antigen Rapid Diagnostic Test IFU.

All results obtained from the investigational device should only be noted in the Case Report Form. These results will not impact or drive patient management decisions. The gold-standard RT-PCR results will provide this information to the healthcare professionals and the enrolled subjects.

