6.2.2 Exclusion Criteria

1. Specimens and testing methods that are deemed not compatible with gold-standard RT-PCR standards.
2. Specimens stored for over 2 hours at 2-8 °C in between collection and testing with EuGeni SARS-CoV-2 Ag RDT
3. Specimens stored for over 5 days at -20°C between collection and testing with RT-PCR.
4. Specimens stored for over 24h at 4°C between collection and testing with RT-PCR.
5. Contamination and/or deterioration of the specimen which, in the opinion of the investigator, may affect its handling and/or analysis.
6. The subject is deemed unsuitable to participate in the study by the investigator.

CONFIDENTIAL

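### Does taking viral load from Ct values, with RT-PCR run to standard of care at up to 10 sites, make the SAP 2.9 subgroup misleading?

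*SAP*

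**What the plan says.** - **SAP 2.9** says subgroup analyses will be made "according to different specimen characteristics, which may include" certain items. One is "The viral load, determined by the Ct value obtained in the RT-PCR analysis". Days from symptom onset is the other visible item. Text before the list and several further bullets are redacted. No Ct band or cut-off is visible.
- **Protocol 4.2.2**: "Specimens to be analyzed by the gold-standard RT-PCR shall follow the procedures established by the standard of care". Redacted text follows directly.
- **Protocol 4.1**: "The CPS will be conducted in up to 10 sites in Europe". It plans 300 positive specimens per arm.
- **Protocol 4.2.1** describes the reference specimen only thus: "another bilateral swab will be taken to be analyzed with the gold-standard RT-PCR". **Protocol 1.1** calls "real-time quantitative polymerase chain reaction (RT-qPCR) from nasopharynx swab the gold-standard", which suggests one swab type without fixing it for this study.
- **Protocol 6.2.2**, criterion 1, excludes "Specimens and testing methods that are deemed not compatible with gold-standard RT-PCR standards".
- **SAP 2.3.1**: "The evaluation of the primary endpoint will be performed using the PP population, analyzing the two arms of the study independently". The visible definitions of sensitivity and specificity there do not use Ct.
- **SAP 2.2.4** plans no regression, so no visible model adjusts for site or assay.

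**The concern.** A Ct value counts amplification cycles and depends on the assay, the gene target and the swab. At full amplification efficiency one cycle is a two-fold difference in template, so assays reading 2 or 3 cycles apart give the same Ct to loads differing 4-fold (2²) or 8-fold (2³). The SAP treats Ct as viral load without visible qualification, and standard-of-care testing at several sites makes more than one assay plausible. Excluding methods not compatible with the gold standard does not put Ct values on one scale.

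At stake is the table showing where an antigen test starts to miss infections. If specimens from different assays share a Ct band, sensitivity at low viral load could look better or worse than it is, and the pooled table alone would not reveal it.

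**Working it through.** **The plan's own figure.** 2 × (300 + 120 + 505) = 1850, which agrees with Protocol 4.1. The 300 positives per arm are the specimens a Ct subgroup would use.

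**Inputs.** From the documents: 300 positives per arm, up to 10 sites, the 80% sensitivity target. Assumed, because the documents give none of them: Ct normal with mean 24 and SD 5; sensitivity p(c) = 1/(1 + exp(0.6 × (c − 28.88))), which averages 0.80; a low-load band of Ct ≥ 30; equal-sized assay groups.

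**Step 1: no offset.** Let W(c) be the share of positives with Ct ≥ c, and S(c) the mean sensitivity among them.

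| c | W(c) | S(c) |
|---|---|---|
| 28 | 0.212 | 0.307 |
| 29 | 0.159 | 0.223 |
| 30 | 0.115 | 0.151 |
| 31 | 0.081 | 0.097 |
| 32 | 0.055 | 0.059 |

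True sensitivity in the band is 15%. The band holds 300 × 0.115, about 35 specimens per arm.

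**Step 2: two assays 2 Ct apart, half the positives on each.** An assay reading d cycles high places a specimen in the band when its reference Ct is at least 30 − d. The pooled value is ΣW(30 − d)S(30 − d) / ΣW(30 − d).

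- Second assay at +2: (0.115 × 0.151 + 0.212 × 0.307)/(0.115 + 0.212) = 0.0825/0.327 = 25%.
- Second assay at −2: (0.115 × 0.151 + 0.055 × 0.059)/(0.115 + 0.055) = 0.0206/0.170 = 12%.
- The same gap centred on the average scale (+1 and −1): (0.159 × 0.223 + 0.081 × 0.097)/(0.159 + 0.081) = 0.0433/0.240 = 18%.

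All three cases have the same gap between assays. The first two also move the average scale, by +1 and −1. The mixing alone takes 15% to 18%; the move of the scale then carries the result to 25% or 12%.

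**Step 3: a single assay everywhere, hence no mixing.** Reading 2 Ct high gives S(28) = 31%; reading 2 Ct low gives S(32) = 6%. A scale shift alone therefore moves the figure either way.

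**Step 4: random offsets with SD 2 Ct, 40,000 draws.** Offsets are either left as drawn or centred within each draw, so that only differences between assays remain.

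| Assays | As drawn: mean (5–95%), share below 15.1% | Centred: 5–95% | Centred: share below 15.1% |
|---|---|---|---|
| 2 | 21% (7–41%), 33% | 15–33% | none |
| 3 | 22% (9–39%), 24% | 15.5–34% (mean 22%) | none |
| 10 | 24.5% (16–34%), 4% | 19–32% | none |

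Centred offsets never took the figure below the true value. An assay reading high moves more specimens into the band, and more detectable ones, than an assay reading low moves out.

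**Step 5: size against sampling error.** The half-width is 1.96 × √(0.15 × 0.85/35) = 0.118, about 12 points. With three assays the average shift is 2, 7 and 13 points at SD 1, 2 and 3. In simulated arms of 300, the order of the Ct bands by sensitivity held in at least 99.7% of runs.

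**Step 6: what tables by assay would give.** With three assays an arm has 300/3 = 100 positives per assay, and 100 × 0.115, about 12, in the band. The exact 95% interval for 2 of 12 is 2–48%, against 5–30% for 5 of 35 pooled.

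**Step 7: primary endpoints.** An offset moves a positive specimen from one band to another. It changes neither the number of RT-PCR positives nor the number the device detects, so overall sensitivity is unchanged.

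**The case for a change.** The strongest case for a change is that Ct really is specific to an assay, that the SAP equates it with viral load without qualification, and that a confidence interval covers sampling error but not the blurring of bands. Viral load is one of only two subgroup characteristics left visible. Recording the assay, gene target and swab type costs little, and assay identity may be hard to recover later. The optional status of the subgroup lowers the stakes but does not make a blurred table right.

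Much of this stands as general good practice. It falls short of a defect in this plan for three reasons. That assays differ, and that Ct will be pooled into common bands, are inferences; the assay, the bands and the case report form content may all be in redacted text, which cannot be counted as missing. SAP 2.7 refers to the reference technique in the singular, though that is weak evidence. And tables by assay would separate the assays without placing any of them on a viral-load scale, at the price of about 12 low-load specimens per table.

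**Conclusion.** No change is called for. The point is a question for the sponsor: are one assay and one reference swab type used throughout? If so, or if redacted text already deals with it, nothing is left of the mixing. If not, an analyst who knows the assay for each specimen would ordinarily label a pooled Ct table as mixing assays and add a descriptive split where cell sizes allow.

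Under the assumed inputs, between-assay differences of SD 2 Ct with three assays lift apparent low-load sensitivity from 15% to about 22% on average. That is less than the sampling half-width of about 12 points; at SD 3 the 13-point shift is about equal to it. The size depends on the assumed slope: with offsets left as drawn at SD 2, three assays take a true 27% to a mean of 33% at slope 0.4, and a true 9% to 17% at slope 0.8. Measured around the assays' average scale, mixing works upward only; error in both directions requires a shift common to all assays, which is not a mixing effect. The figures show direction and rough size and are not estimates for this study. Primary sensitivity and specificity are not affected by the banding.
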